#### IIIC.4f. Methods

**IIIC.4f.1. Overview:** A description of the protocol/procedures is provided (IIIC.4f.2 - IIIC.4f.6; **Fig 6, Table 1**). Eleven-to-thirteen year-old AA youth and their parents will complete information on demographic and health status as part of their clinic visits. Families selected randomly from the eligible pool will be invited to participate, while at the clinic or later via mail (**IV.A.2a, Human Subjects**). Research is an integral part of these participating clinical programs and processes are in place for a smooth transition from clinical care to research that follows the Institutional Review Board and Health Insurance Portability and Accountability Act (HIPAA) guidelines. When contact is made, they will be provided information about the study, with an overview of the time commitment and assessments. Interested families will be screened further to determine eligibility by obtaining medical, psychiatric and treatment history.

**Phase 1 (Pre-intervention Assessments):** Information on psychiatric symptoms, psychosocial factors and risky behaviors will be completed. Those who meet eligibility criteria will have a blood draw for gonadal hormones and receive training on the fMRI tasks and have a mock scan. A urine sample will be obtained to test for alcohol/drug use and pregnancy. They then will complete baseline fMRI studies. **Phase 2 (Intervention Phase):** The families will be randomized using procedures described in IIIC.4f.5 to PAAS or wait-list condition (1:1 ratio) for the 6-week intervention period. PAAS consists of 6 web- or DVD-based weekly sessions, 90 minutes per session; the first half includes individual, concurrent curricula for caregivers and youth, and the second half is a family-joint session designed for practicing the skills learned in the individual sessions. At the end of the 6-week intervention period, the urine drug test and fMRI studies will be repeated in both groups. **Phase 3 (Follow-up Phase):** Three months after the intervention phase, both psychosocial and risky-behavior assessments will be repeated. The wait-list group then will be offered the PAAS intervention as a benefit for participation in the study.

## IIIC.4f.2. Measures for Primary Hypothesis Testing

**IIIC.4f.2a. Youth Psychological Protective Processes:** This index consists of seven measures (**Appendix 1**).

**IIIC.4f.2a.1. Resistance Efficacy:** Participants respond to three versions of a scenario to report the actions they believe they would take if presented with the chance to drink alcohol, smoke cigarettes or use marijuana.

**IIIC.4f.2a.2. Self-control:** The 25-item Self-Control Inventory includes items of good self-control (e.g. delay of gratification, planning, problem-solving, dependability, and soothability) and poor self-control (e.g. impulsivity, immediate gratification, distractibility, and low frustration tolerance).

**IIIC.4f.2a.3. Future Orientation:** The Time Perspective Inventory consists of the future, present/hedonistic, and present/fatalistic subscales. The future subscale reflects formulation of goals and plans to achieve them.

**IIIC.4f.2a.4. Emotion Regulation:** On the Coping Processes Inventory, respondents are provided definitions of various coping behaviors and asked how often they use each approach for dealing with problems concerning school, parents, health and sadness.

**IIIC.4f.2a.5. Self-image:** Body Image subscale from the Sexual Self-concept Inventory consists of eight items that index the youth's evaluation of his/her own physical appearance.

**IIIC.4f.2a.6. Self-esteem:** Rosenberg Self-esteem Scale includes a 5-item general positive self-esteem subscale and a 5-item general negative self-esteem subscale.

**IIIC.4f.2a.7. Impulsivity:** Eysenck Impulsiveness Scale includes 13 items that assess personality traits related to impulsivity and venturesomeness.

## IIIC.4f.2b. Neuroimaging Protocol

**IIIC.4f.2b.1. Mock MRI Scan:** At the baseline assessment, participants will be provided take-home information that will help to prepare them for MRI scanning. They will complete a mock scan to practice staying still in the scanner, get used to the noise and practice the fMRI tasks. This also will allow us to assess for claustrophobia.

**IIIC.4f.2b.2. Data Acquisition:** Neuroimaging data will be acquired on a 3 Tesla Philips Achieva MRI scanner with a 32-channel head coil located at Vanderbilt University Institute of Imaging Science (VUIIS; **letter from [name]**). Padding behind the head and neck will be used to increase comfort, and the forehead will be strapped to prevent head motion. A 20-25 minute break will be provided between resting and task-based scans to reduce motion artifacts and impaired performance on the task. To correct for the confounding effect of overlapping physiological signals, pulse and respiration will be measured with MRI-compatible non-invasive equipment. In our multi-modal imaging protocols lasting 60-90 minutes, we had reliable data in 93%-97% of the samples.

A high-resolution T1-weighted scan (1 mm isotropic resolution; 6.5 min) will provide anatomical information to serve as a basis for cortical parcellation and a template for registering the functional imaging data. This will be followed by a B0 mapping sequence (1 min) to correct image distortions due to magnetic field errors. Next, resting-state (rs-fMRI) scans will be obtained to measure intrinsic functional connectivity. T2\* weighted BOLD images with a voxel size of 3mm isotropic and a volume acquisition time of 2 sec will be acquired using a 2D gradient echoplanar imaging (EPI) sequence over 12 min (360 image volumes) to obtain more reliable data. Participants will be instructed to relax with their eyes open and to look at a fixation cross. They will be monitored with eye-tracking equipment to ensure that they do not fall asleep. For task-based fMRI scans (45 min), stimulus presentation will occur with E-Prime, with the images projected onto an overhead LCD panel. A 5-button box will be used for recording behavioral data. Functional images will be acquired with a gradient-echo, EPI sequence: 34 oblique axial slices (3 mm thick, 0 mm gap), oriented to the AC-PC line and encompassing the entire cerebrum

Phase Window	Informant	Duration	Screen	Phase 1		Phase 2 - Intervention					Phase 3	
				5-10 Days		Starts within 14 Days of Screen						
				1	2	3	4	5	6	7	8	
Visit	Parent	Youth	Minutes			Wk 1	Wk 2	Wk 3	Wk 4	Wk 5	Wk 6	
Intervention Week												
Clinic/Telephone Screen	X	X	15-30	X								
Informed Consent/Assent	X	X	45-60			X						
Demographic Information	X		10-20			X						
Psychiatric Diagnostic Screen	X	X	30-60			X						
Youth Beh/Emotional Problems	X	X	20-30			X						
Reward-drive Traits		X	15-20			X						
Risky Behaviors		X	15-20			X						
Resistance Efficacy		X	10-15			X						
Self-control		X	15-20			X						
Future Orientation		X	10-15			X						
Emotion Regulation		X	5-10			X						
Self-image		X	5-10			X						
Self-esteem		X	5-10			X						
Impulsivity		X	5-10			X						
Involved-vigilant Parenting	X	X	10-15			X						
Risk-behavior Communication	X	X	10-15			X						
Adaptive Racial Socialization	X	X	10-15			X						
MRI Safety Screen	X	X	5-10			X						
Handedness Scale		X	5-10			X						
Tanner Stages		X	5-10			X						
Serum Gonadal Steroids		X	10-15			X						
Urine Alcohol/Drug Test		X	10-15			X						
Urine Pregnancy Test		X	0			X						
Task Practice/Mock Scanner		X	60-90			X						
Resting and Task-based fMRI		X	90-120			X						
PAAS Intervention	X	X	90-100			X	X	X	X	X	X	

and most of the cerebellum (TR/TE = 2000/25 msec, FOV = 24 cm, matrix = 64 × 64). This sequence was designed to preserve the signal in the striatum and ventral PFC, areas which are susceptible to signal drop-out. An automated higher-order shim procedure will be applied to minimize potential magnetic field inhomogeneities.

**IIIC.4f.2b.3. The WOF Task:** This task allows for the analysis of both risk-seeking and risk-avoidance (Fig 7). During each trial, the participants will be shown a wheel on which the probabilities of winning and losing points are shown as pink and yellow sections, respectively. The number of points that can be won or lost is printed on the wheel sections. The words “Bet” and “Pass” are displayed each time, prompting participants to select one or the other. For the present study, this “decision phase” is the period of interest. After 3 seconds, the wheel spins for a variable, randomly jittered period (1, 3, 5, or 7 sec), and the final result is displayed for 1 sec. If participants choose to bet, and the wheel lands on the pink section, they win the points indicated. Conversely, if the wheel lands on the yellow section they lose the number of points shown. These amounts will be added (or subtracted) to a running total that is not revealed until the end of the task. If participants choose to pass, they still see the outcome but no points will be added or deducted.

Win amounts are kept constant while probability and loss amounts are manipulated orthogonally resulting in 6 different wheels that represent 4 win/loss ratios (100/0, 60/40, 40/60, 0/100) and 2 levels of expected value (EV; +12 and -12). Participants are not explicitly told about the uniformity of expected values. The 0/100 wheel (100% chance of losing 12 points) and the 100/0 wheel (100% chance of winning 12 points) serve as no-risk control conditions and each is presented 8 times. Each 40/60 and 60/40 wheel (EV+ and EV-) is presented 22 times across 4 blocks. Behavioral outcomes include risk-seeking (percent of trials betted), risk-avoidance (percent of trials passed), and response times across conditions of varying probabilities and expected values. We found no practice effects with repeated tasks in at-risk adolescents during longitudinal follow-up ([name], unpublished data).

**IIIC.4f.2b.4. Go/No-Go Task:** The task assesses behavioral responses, with the subjects selectively responding to target stimuli (“X” ~.80 probability) and inhibiting responses to infrequent non-target stimuli (“K”~.20 probability; **IIIC.3d**). The task consists of two runs, with 245 trials per run (7 min) and a random inter-stimulus interval.

**IIIC.4f.2b.5 Quality Assurance (QA):** Weekly QA data will be collected using the American College of Radiology Phantom Test Guidance Manual. The Functional Biomedical Informatics Research Network QA protocol will be used so that changes in image characteristics over the study period can be monitored and corrected.

**IIIC.4f.2b.6. fMRI Data Processing and Analysis:** Each participant's functional images (rest and task) will be corrected for head motion and co-registered to a common atlas space, then smoothed with a 6 mm kernel. After initial pre-processing, the time series at each voxel will have white matter, cerebrospinal fluid and motion-related signals removed via regression, and will be low-pass filtered at 0.1 Hz to retain low frequencies relevant for connectivity estimation. Head motion can still be a significant confound in fMRI connectivity studies, particularly in children. Hence, we will identify volumes that show large displacement (>0.5mm) or large change in global signal (>0.5%) relative to the preceding volume, and remove them prior to connectivity analysis. [The resulting 3 metrics can be summarized to a single number and then compared between groups or used as covariates.]

For the task-based data, event-related neural responses will be modeled with separate canonical hemodynamic response functions for each of the conditions (e.g. wheel types). For instance, BOLD responses to Risk vs. No-Risk trials will be compared, within/across probabilities and expected values. Group-level analysis will compare the trials during which the participants passed the trials (risk-avoidance) to trials where they bet. For the Go/No-Go task, successful Go trials will be compared to both successful and unsuccessful No-Go (inhibition) trials.

Resting-state functional connectivity will be calculated as the Z-transformed correlation coefficient between pre-processed time series, using the CONN toolbox. Connectivity between seed region time series and each gray matter voxel will be calculated to create connectivity maps for each seed region. Task-based connectivity will be calculated using the gPPI toolbox. For both types of connectivity, we will use seed-region approaches with the following seeds: inferior and superior parts of the ventral striatum, ventral and dorsal parts of the ACC, mPFC, OFC and DLPFC. Seed regions will be defined using probabilistic atlases derived from structural tracings. Connectivity maps for each seed region will be compared at each voxel among the groups, using a restricted maximum likelihood approach that accounts for heteroskedasticity (SPM8 software implementation). The resulting T maps will be thresholded at  $p < 0.05$ , correcting for the multiple voxel comparisons based on spatial smoothness using random field theory, to identify brain regions where the groups differ in connectivity.

In addition to hypothesis-driven seed-based functional connectivity of fronto-striatal circuits, the Wager/Lindquist Multilevel Mediation and Moderation (M3) Toolbox will be used in conjunction with SPM and MATLAB to conduct whole-brain mediation analysis. This analysis allows voxels to be identified that make the strongest case for mediation or search for maps of each effect in the mediation.

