5	Protecting against dangerous behavior	Understand risk prevalence, overall and for your community; Importance of being an approachable parent	Peer pressure; parents' concerns about peer affiliation	Identify peer pressure; compare risk engagers from non-risk engagers; dealing with temptation; prosocial peer affiliation	Caregivers and youth working together to protect youth from risk behaviors	Develop family plan for handling peer pressure and temptation; share expectations and values about risk and friendship
6	Parental protections that reduce high risk behaviors	Learn how to effectively monitor youth; understand the prevalence of sexual activity in teens; establish expectations about sex	Dealing with sexual and substance use temptations	Identifying and avoiding dangerous situations; connecting temptations, dreams, goals, school and future orientation	Our family plan and pledge for positive youth development	Share expectations, dreams, and hopes; discuss/identify family strengths; establish a family creed of strength, growth and competence

**IIIC.5. Primary Outcome Criteria:** Primary outcome variables include fronto-striatal functional connectivity at rest and while performing the WOF task and youth psychological protective factors (cognitive and emotional self-regulation). Other neural measures/circuits, psychological/social-contextual and behavioral variables (**Appendix 1**) will be used either as supplementary measures or as potential covariates. By sharpening our focus to *a priori* specified neural circuits and psychological measures, we hope to increase statistical power and, in turn, our ability to identify important differences in the responses of these circuits according to youth protective factors.

**IIIC.6. Sample Attrition:** The team has experience with intensive longitudinal studies involving difficult-to-reach samples with retention rates exceeding 90% for short-term follow-up (**IIIC.10a**). Even with a liberal estimate of 20% attrition, we will have 102 participants, which will give us sufficient power to detect medium effects (**IIIC.7e**).

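### If flagged volumes are cut from the WOF task runs before gPPI, the natural reading of the single rest-and-task pipeline, the task connectivity estimate is attenuated more in youth who move more

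*Combined protocol and SAP*

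**What the plan says.** Section IIIC.4f.2b.6 starts from both kinds of scan: "Each participant's functional images (rest and task) will be corrected for head motion". It continues, without narrowing the scope, to nuisance regression at each voxel, after which the series "will be low-pass filtered at 0.1 Hz to retain low frequencies relevant for connectivity estimation". Volumes with displacement above 0.5 mm or a global signal change above 0.5% are then identified "relative to the preceding volume, and remove them prior to connectivity analysis". The motion metrics "can be summarized to a single number and then compared between groups or used as covariates".

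The same section later uses the word connectivity for both types of analysis: CONN for rest, and for the task "Task-based connectivity will be calculated using the gPPI toolbox". Its paragraph on task data covers the event-related model and the contrasts. It gives no separate filter, no censoring method and no minimum amount of retained data.

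Section IIIC.5 makes the result a main endpoint: "Primary outcome variables include fronto-striatal functional connectivity at rest and while performing the WOF task". Section IIIC.7d.1 fits separate Hypothesis 1 models for rest and task, and section IIIC.7d.2 uses neural responses as mediators for Hypothesis 2.

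**The concern.** A resting correlation does not depend on the order of the samples, so deleting volumes is workable there. gPPI does depend on it. It deconvolves the seed series to an estimated neural signal, multiplies that by the trial timing, and re-convolves the product with the haemodynamic response function (HRF). Each step assumes samples one TR apart. Once volumes are cut and the ends joined, neighbouring samples are no longer 2 s apart, and every response window that crosses a join is wrong.

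The loss then varies from youth to youth with head motion. At stake are the sensitivity of one of the two Hypothesis 1 models and the quality of a candidate Hypothesis 2 mediator, in 11-13 year-olds, an age at which the plan itself regards motion as a serious confound.

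The 0.1 Hz cut-off is a second, smaller matter. It is stated for connectivity in general, with no separate setting for an event-related task.

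**Working it through.** **Inputs from the plan.** TR is 2 s (IIIC.4f.2b.2). A WOF trial is a 3 s decision, a spin of 1, 3, 5 or 7 s (mean 4 s) and a 1 s result (IIIC.4f.2b.3). There are 4 risky wheels x 22 = 88 trials and 2 no-risk wheels x 8 = 16.

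- Mean trial: 3 + 4 + 1 = 8 s, a rate of 1/8 = 0.125 Hz.
- Task length: 104 x 8 = 832 s, or 832/2 = 416 volumes. Removing 5%, 10% or 20% means about 21, 42 or 83 volumes.

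**The plan's own figure.** IIIC.7e states a detectable r = .31 (R² = .10) at N = 102, two-tailed alpha .05, 80% power. An omnibus regression test with 3 predictors gives R² = .1001 and power .799 at R² = .10, so it reproduces; the number of predictors is not stated. For a 1-df group effect the detectable r is .27, and power at r = .31 is .90. The plan gives no figure for loss from scrubbing or filtering.

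**Deletion before gPPI.** Three simulations estimated the Risk minus No-Risk gPPI effect. Deletion is with design rows cut to match. The reference for each is the intact series.

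| Volumes removed | A | B | C |
|---|---|---|---|
| 5% | 0.96-0.97 | 0.87 | 0.96-0.99 |
| 10% | 0.87-0.93 | 0.77 | 0.92-0.98 |
| 20% | 0.73 | 0.62 | 0.84-0.90 |
| 30% | not run | 0.46 | not run |

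A used scattered deletions, two noise levels and 300 runs per setting (Monte Carlo SE 0.03-0.05). B used two-volume bursts and 150 runs (SE about 0.03). C is a third, separate set. In B, leaving the design on its original clock after deletion left 0.15 or less of the effect.

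**Intact series with censoring.** In B, keeping every volume through deconvolution and censoring flagged volumes in the model gave 0.99 at both 10% and 30% flagged; C gave 0.99-1.00. Only precision fell: in B, mean/SD went from 3.1 to 2.9 (10%) and 2.5 (30%). With deletion it fell to 2.1 and 1.2.

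**Low-pass.** The trial rate exceeds the cut-off, but jitter and the HRF put most regressor variance below it. The share above 0.1 Hz is about 6% for the gPPI term, 11-13% for risky trials and 16-20% for all trials. With no deletion, the filter left 1.11 of the coefficient in B and 0.92 in C; A put the added loss at 0-9%. Precision fell (B: mean/SD 3.1 to 2.7).

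**What attenuation could cost.** If the correlation in the Hypothesis 1 test shrank in the same proportion, 1-df power at N = 102 would be:

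- x0.9: r = .279, 83%
- x0.8: r = .248, 73%
- x0.7: r = .217, 60%

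This supposes that the spread between youth does not shrink with the effect, so it is illustrative.

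**Bias between arms.** Let c be the true mean contrast, equal in both arms, and k the fraction kept. The spurious arm difference is (k_PAAS - k_wait-list) x c. With B's values at an assumed 10% and 20% removed, it is (0.77 - 0.62)c = 0.15c. It is zero if motion is equal in the arms, and it changes sign with c.

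**The case against.** - **The rule may not mean cutting.** Removing a volume can mean censoring it inside the model, and that gave no attenuation. The mention of rest and task is attached to motion correction, co-registration and smoothing, and no sentence addresses gPPI by name. This stands to the extent that attenuation is conditional. But censor regressors act within the gPPI model, whereas the plan removes volumes ahead of it, and nothing exempts the task runs. Cutting is the more natural reading.
- **The low-pass.** A reader might infer that a 0.125 Hz trial rate above a 0.1 Hz cut-off means the filter itself attenuates the task effect. The calculations do not support that: about 94% of the gPPI term's variance lies below the cut-off, and the coefficient moved in different directions across simulations.
- **A false positive for Hypothesis 1.** A reader might also infer that treated youth would lie stiller at week 6 and so show higher connectivity with no neural change. The documents report no motion difference by arm and give no sign for the mean contrast. With a negative contrast, the same mechanism would work against Hypothesis 1. Without a difference in motion, randomisation makes the loss equal on average, and the cost is power.
- **Safeguards exist.** The plan has a mock scan, padding, a forehead strap and a break, and reports reliable data in 93%-97% of earlier samples. These reduce flagging but do not say how flagged volumes enter gPPI. The motion summary is optional and is not named among the covariates in IIIC.7d or IIIC.7d.1. It could adjust for a mean difference linked to motion, but would not restore a coefficient shrunk within each youth's own model.
- **The sizes vary.** True: flag rates, burst pattern, noise and regularisation are assumed. Direction and dose-response agree in all three simulations. Clustering cannot be counted on to soften the loss, since B, with two-volume bursts, showed the largest.

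**Conclusion.** The concern holds in conditional form. The plan applies one low-pass and one volume-removal rule to rest and task alike. If volumes are cut before gPPI, the WOF connectivity estimate is attenuated, and more so in youth who lose more volumes. The remaining effect is roughly 0.87-0.99 at 5% removed, 0.77-0.98 at 10% and 0.62-0.90 at 20%, against about 0.99-1.00 with an intact series and censoring. The documents give no flag rate, so these ranges show scale and do not predict this trial.

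The main consequence is reduced sensitivity and motion-dependent measurement of a primary outcome. The low-pass mainly costs precision on task runs, and its effect on the coefficient is uncertain. Bias between arms arises only if motion differs by arm, and its direction depends on the sign of the contrast. The documents do not support saying that attenuation is certain or that the pipeline would imitate a PAAS effect. The change is still worth making, because a better method is available at almost no cost.

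**What to change.** In IIIC.4f.2b.6, limit volume deletion and the 0.1 Hz low-pass to the resting-state runs. For the WOF runs, state that every volume stays in place through deconvolution, that only a high-pass filter is used (cut-off to be stated, for example 1/128 Hz), and that each flagged volume gets one censor (spike) regressor in the first-level and gPPI models. Say also which rule the Go/No-Go runs follow; that task is supplementary and was not simulated.

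The cost is two sentences and a toolbox setting, with no new data. Each flagged volume uses one degree of freedom, the same as deletion. Some high-frequency noise that the low-pass would have removed stays in the task data.

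### As the processing steps read, high-motion volumes are removed only after the 0.1 Hz low-pass filter, which leaves part of each motion spike in the retained resting-state data

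*Combined protocol and SAP*

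**What the plan says.** Section IIIC.4f.2b.6 covers rest and task images together. After realignment, registration and smoothing, "the time series at each voxel will have white matter, cerebrospinal fluid and motion-related signals removed via regression", "and will be low-pass filtered at 0.1 Hz to retain low frequencies relevant for connectivity estimation". The next sentence reads: "Head motion can still be a significant confound in fMRI connectivity studies, particularly in children". As a consequence, the plan flags volumes with displacement above 0.5 mm or a global signal change above 0.5% "relative to the preceding volume, and remove them prior to connectivity analysis". A motion summary may then be compared between groups or used as a covariate; this is optional.

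The resting scan has "a volume acquisition time of 2 sec" and runs "over 12 min (360 image volumes"); the task scans use "TR/TE = 2000/25 msec". Resting connectivity is the Z-transformed correlation of the pre-processed series, and task connectivity comes from gPPI. Section IIIC.5 makes fronto-striatal connectivity at rest and during the WOF task a primary outcome. It is the dependent variable for Hypothesis 1 (IIIC.7d.1) and the mediator for Hypothesis 2 (IIIC.7d.2).

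The section does not give the filter type. It does not say whether flags are set on filtered or unfiltered data, whether flagged volumes are censored or interpolated before the filter, or whether neighbouring volumes are also dropped.

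**The concern.** A low-pass filter replaces each volume by a weighted average of the volumes around it. If a motion spike is still present when the filter is applied, part of it moves into adjacent volumes that no rule flags. Deleting the flagged volume afterwards cannot recover that part. Where the same artefact reaches two regions, the leftover raises their correlation.

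This affects a primary outcome in 11-13 year-olds, an age group in which the plan itself expects motion to matter. The direction also matters: Hypothesis 1 predicts increased connectivity, and shared artefact pushes the resting measure the same way. If the arms moved to different degrees at the second scan, part of a group difference could be artefact. If they did not, the cost is extra noise in the outcome and the mediator.

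**Working it through.** **Inputs from the plan.** 2 s per volume, a 12-minute resting run, a 0.1 Hz cut-off, and flagging by change from the previous volume. Filter type, spike size and spike frequency are not given, so they are assumed below.

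**Reproducing the stated run length.** 12 × 60 / 2 = 360 volumes, as stated. The Nyquist frequency is 1/(2 × 2) = 0.25 Hz.

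**Spread of a one-volume spike, ideal filter.** The run lasts 720 s, so frequencies are spaced 1/720 Hz apart and 0.1 Hz is the 72nd. The filter keeps 2 × 72 + 1 = 145 of 360 components, or 0.403. A spike of height 1 becomes 0.403 at its own volume. At lag k it is close to sin(0.4πk)/(πk); the values on the finite series are 0.304 at ±1 and 0.091 at ±2.

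**Energy left after deletion.** Total filtered energy is 0.403. The spike volume holds 0.403² = 0.162 and each immediate neighbour 0.304² = 0.092.

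- One volume deleted: (0.403 − 0.162)/0.403 = 60% remains.
- Departure and return volumes deleted: (0.403 − 0.162 − 0.092)/0.403 = 37% remains.

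The second case is what the written rule gives for an isolated excursion, because both the jump away and the jump back are large changes from the previous volume.

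**A gentler filter.** A second-order zero-phase Butterworth filter gives 0.408, 0.282 and 0.067 at lags 0, 1 and 2, with 51% (0.507) of the energy outside the spike volume. Total energy is 0.408²/(1 − 0.507) = 0.338. With both volumes deleted, 1 − (0.408² + 0.282²)/0.338 = 27% remains. The leakage does not depend on the ideal filter, though its size does.

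**Effect on the resting correlation.** Two 360-volume series were simulated with true z = 0, autocorrelation 0.3 and positive shared spikes of 3 SD (all assumed), using the ideal filter and no nuisance regression. Bias in Fisher z when volumes are filtered and then removed:

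| Volumes with a spike | One volume deleted | Departure and return deleted |
|---|---|---|
| 2% | +.07 | +.04 |
| 5% | +.15 | +.10 |
| 10% | +.25 | +.17 |

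A separate run of the two-volume case gave about .04, .09 and .18. For scale, the within-scan sampling SD of z is about .10.

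**Does the order cause it?** A second simulation used true r = 0.30 and shared spikes of random sign, deleting one volume per spike. With 5% of volumes affected and spike SD 4, mean r was 0.503 with no removal, 0.439 with removal after filtering, and 0.302 when flagged volumes were interpolated before filtering and dropped afterwards. The spike-free value was 0.301. In every setting tried, the re-ordered pipeline came within 0.002 of the spike-free value. At the mild end (2% of volumes, spike SD 1), late removal gave 0.295 against 0.291, which is negligible.

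**Allowing for nuisance regression.** With 5 SD spikes in 2/5/10% of volumes and one volume deleted, bias was .16/.34/.52 without regression. It was .09/.10/.11 when the nuisance signals carried the spike with noise of half the signal SD, and .15/.23/.28 when they were noisier.

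**The case against.** **The order is inferred.** The only explicit timing for removal is that it precedes connectivity analysis. Regression and filtering that already take account of censored volumes would fit those words, and the plan cites a source for its censoring method and names a connectivity toolbox, neither of which can be consulted here. This stands in part. A reader might infer that the plan firmly commits to censoring last; it does not. Removal after filtering is the natural reading, because removal is introduced as the response to motion left after the preceding steps. On the kindest reading the order is unstated, and the remedy is the same.

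**Most of the spike is removed.** A reader might infer that deletion leaves most of the artefact behind. For an isolated excursion under the written rule this is wrong: about 37% stays. The 60% figure applies only if a single volume is flagged, for example when a lasting displacement comes with a one-volume artefact.

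**Regression comes first.** Only spikes that survive it are spread, so the tabulated biases are too high wherever it works well. This stands, although the plan concedes that some motion remains.

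**Filtered data might hide spikes from the global-signal rule.** This is tempting, but no section says the global signal is computed after filtering, and the displacement rule would be unaffected.

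**Other protection exists.** Randomization, a mock scan, padding and strapping, a break between scans and the motion summary all help. They reduce motion or may allow adjustment for it; they do not undo leakage, and use of the summary is optional.

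**Conclusion.** The point holds as a matter of processing order. As the section reads, late removal leaves part of each residual motion spike in the retained resting-state volumes: about 37% of its filtered energy when departure and return are both flagged and about 60% when one volume is, both for an ideal filter. Where the artefact is shared, each participant's resting correlation is inflated. The documents do not fix the size. It runs from negligible to roughly +.04 to +.18 in Fisher z for 3 SD spikes in 2-10% of volumes, before any reduction by nuisance regression.

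Two stronger conclusions are not supported. A reader might infer that the Hypothesis 1 group comparison is biased. That requires motion at the second scan to differ between arms, and the documents give no evidence that it will; otherwise the effect is mainly noise. A reader might also extend these figures to the task outcome. That outcome uses gPPI in a separate model, and its sensitivity was not calculated.

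The point is worth acting on because a primary outcome and the mediator depend on it and the remedy is cheap.

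**What to change.** In IIIC.4f.2b.6, state the filter and this order:

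1. Flag volumes on realigned, unfiltered data.
2. Exclude flagged volumes from the nuisance regression, using spike regressors, and interpolate them.
3. Apply the 0.1 Hz low-pass filter.
4. Drop the flagged volumes before computing correlations.

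Apply the same flagging rule to rest and task scans. The flagged volumes themselves cannot be the same, because the scans are separate acquisitions. It would also help to make the comparison of the motion summary between arms definite, since differential motion is the condition under which the group contrast becomes biased.

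The cost is a re-ordered pipeline and a few sentences of wording. No new data are needed, and scans already acquired can be reprocessed.
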